1.0 INTRODUCTION AND STUDY RATIONALE

Glioblastoma is the most common primary malignant type of brain tumor in adults (2). Surgical tumor resection followed by chemoradiation therapy is the standard of care for patients with glioblastoma, but its prognosis is still fairly dismal (median survival time = 15 months) (3, 4). One major concern that prevents effective treatment management is the difficulty of differentiating between pseudo-progression and true-progression (5). Pseudo-progression occurs in about 20-30% of glioblastoma patients typically within 3 months after radiotherapy with or without chemotherapy has been completed (6). Pseudo-progression is a local inflammatory reaction caused by irradiation and enhanced by concurrent chemotherapy, which leads to a transient increase of blood brain barrier (BBB) permeability (7, 8). The BBB, however, is also disrupted by neoplasm (9). Therefore, both pseudo- and true-progressions appear with an increased contrast enhancement in MRI, and there are currently no established techniques to differentiate between them (5). Pseudo-progression is typically known to be associated with better clinical outcomes (10). Thus, as illustrated in Fig. 1, pseudo-progression mistaken for true-progression results in the discontinuation of an effective therapy, while true-progression mistaken for pseudo-progression leads to the continuation of an ineffective therapy that may induce adverse side effects.

[figure not shown]

Fig. 1. Misdiagnosis of glioblastoma progression. Pseudo-progression mistaken for true-progression results in the discontinuation of an effective therapy, while true-progression mistaken for pseudo-progression leads to the continuation of an ineffective therapy.

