The data reproducibility across two different scanners assesses between-scanner variability combined with the inaccuracy of region of interest (ROI), arterial input function (AIF) and image co-registration. The tumor ROI will be determined by [name] (a neuro-radiologist; co-I) (see "ROI determination" section for the details). The ROIs of two scans of each subject will be matched as closely as possible to minimize intra-observer variation. We recently introduced a novel method to reliably measure individualized AIFs (36) which will be employed in this study. If the patient moves during imaging, a similarity transformation (37) will be used for 3D coregistration. The pharmacokinetic (PK) parameters (e.g., K^{trans}) within the ROI will be averaged at each scan after P4-based error correction, and the mean values of two scans will be compared to calculate the reproducibility coefficient (%RDC) using the equation, %RDC=2.77wCV, where wCV is the within-subject coefficient of variation (38). The %RDC before P4-based error correction will also be calculated for comparison. Data reproducibility will be assessed using the intra-class correlation coefficient (ICC) as well. $ICC = \sigma^2 b / (\sigma^2 b + \sigma^2 w)$, where σb is between-subject standard deviation and σw is within-subject standard deviation.

Each tumor will be classified into pseudo- or true-progression based on the histopathologic data or RANO criteria. We expect approximately 40-50% of glioblastoma will be classified to

pseudo-progression, as demonstrated in previous studies (11-13). All PK parameter maps will be created within a month after image acquisition so that the image processing will not be biased by subsequent clinical findings. We will examine whether the difference of tumor PK parameters between pseudo- and true-progressions will become more statistically significant after P4-based error correction.

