4.0 SELECTION OF PARTICIPANTS

4.1 Number of Participants

We plan to accrue 12 patients at the University of Alabama at Birmingham (UAB). UAB has a total of 11 neurosurgeons for adult patients, seeing about 60 patients with recurrent glioblastoma annually. We presume that at least 16% of them will agree to participate in this study judging from our previous experience in patient enrollment.

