8.0 STATISTICAL METHOD

> Sample Size Justification

Aim 1. The K^{trans} reproducibility measured by the ICC was 0.99 in our previous experiment ($\underline{1}$), when the P4 was used for error correction (3 volunteers x 4 tissues = 12 measurements) (see **Fig. 3C**). For brain DCE-MRI, however, the perfusion value can only be assessed in the tumor region. Thus, to achieve greater than 90% power to confirm that the data repeatability measured by the ICC is larger than 0.9 with 5% type I error, at least 12 volunteers will be needed.

Aim 2. In Yun et al's study (13), the difference of tumor K^{trans} between pseudo- and true-progressions was 91% with the standard deviation (SD) of approximately 50% in each group (p=0.004). If the mean and SD of each group in the proposed study will be the same with those of Yun et al's study (0.44±0.25 vs 0.23±0.10 min⁻¹), the sample size (n=12) will have 55% power at a 5% significant level to differentiate the two groups (assuming n=6 per group) using a one-side two-group student t-test. However, if the SD is reduced to ≤35% using the P4, the power will be increased to ≥90%.

> Statistical Analysis

Descriptive analysis with the mean and SD will be presented for each experimental parameter and each time point. Graphic presentation will be considered when appropriate. Due to repeated measurement, ANOVA analysis with a mixed model will be used to estimate the measurement error (within error) with two-sided 95% confidence interval (49). Data

reproducibility will be assessed using both the ICC and %RDC (33). Tumor PK parameters between pseudo- and true-progressions will be compared using two-group student t-test (50). Data will be transformed using natural logarithms if the variability is found to be dependent upon its mean value. All data will be analyzed using SAS (SAS institute, Cary, NC) by [name] (see her support letter).

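### Aim 2 power is quoted only for an exact 6/6 split, the upper edge of the plan's own expected range; averaged over that range it is about 46–53%, not 55%

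*Combined protocol and SAP*

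**What the plan says.** Section 8.0 (Sample Size Justification, Aim 2) takes planning values from a cited glioblastoma DCE-MRI study, "0.44±0.25 vs 0.23±0.10" per minute, and concludes that "the sample size (n=12) will have 55% power at a 5% significant level to differentiate the two groups (assuming n=6 per group". The calculation uses a one-sided two-group Student t-test. It adds that power reaches at least 90% if the phantom correction brings the SD down to 35% or less. No other split is considered.

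Section 3.1 describes how the groups arise: "Each tumor will be classified into pseudo- or true-progression based on the histopathologic data or RANO criteria". It also says "We expect approximately 40-50% of glioblastoma will be classified to" pseudo-progression, citing three earlier studies. Section 4.1 says "We plan to accrue 12 patients". Patients enter while it is still unclear which kind of progression they have, and nothing in the protocol fixes, stratifies or tops up either group.

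**The concern.** Group membership is an outcome here, so the investigators cannot choose 6/6. A 40–50% share of 12 patients is 4.8 to 6.0 pseudo-progressions, which puts 6/6 at the upper end of what the plan itself expects.

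The planning SDs are also unequal. Section 1.0 says true progression shows the higher perfusion, so 0.44±0.25 belongs to true progression and 0.23±0.10 to pseudo-progression. With fewer pseudo-progressions, the pooled SD moves towards 0.25 and the named test loses power.

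Differentiating the two kinds of progression is the primary goal (section 2.1), and Aim 2 holds the only power statement for it. The same 6/6 assumption sits under the figure of at least 90%, on which the case for the correction rests.

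**Working it through.** **Inputs.** From section 8.0: means 0.44 and 0.23 (difference 0.21), SDs 0.25 and 0.10, one-sided 5%, pooled t-test with 10 df. From section 4.1: n = 12. From section 3.1: pseudo-progression share p = 0.40 to 0.50. Assumption: patients are independent, so the number of pseudo-progressions is Binomial(12, p).

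**1. The plan's own figure.** At 6/6 the pooled SD is √((0.25² + 0.10²)/2) = 0.190. The noncentrality is 0.21 / (0.190 × √(1/6 + 1/6)) = 1.91 and the critical value is 1.812. Noncentral t power is **55.3%**, which matches the stated 55%. Simulation with each group's own SD gives 56.1%; the formula puts one SD in both groups.

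**2. Other splits.** Pooled SD = √(((n_true − 1) × 0.25² + (n_pseudo − 1) × 0.10²)/10). Power and type I error are simulated for normal data with each group's own SD, one-sided 5%.

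| Pseudo/true | Pooled SD | Power, pooled t | Actual type I error, pooled t | Power, Welch |
|---|---|---|---|---|
| 7/5 | 0.176 | 59% | 8.2% | 46% |
| 6/6 | 0.190 | 56% | 5.7% | 53% |
| 5/7 | 0.204 | 51% | 3.8% | 57% |
| 4/8 | 0.216 | 43% | 2.2% | 60% |
| 3/9 | 0.228 | 32% | 1.2% | 59% |

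**3. How likely the splits are.**

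| | p = 0.40 | p = 0.45 | p = 0.50 |
|---|---|---|---|
| Exactly 6/6 | 18% | 21% | 23% |
| 4 or fewer pseudo | 44% | 30% | 19% |

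**4. Average power.** Average = Σ P(k pseudo) × power at k. For p = 0.40, with k = 2 to 10: 0.0639×0.186 + 0.1419×0.319 + 0.2128×0.425 + 0.2270×0.506 + 0.1766×0.561 + 0.1009×0.594 + 0.0420×0.612 + 0.0125×0.614 + 0.0025×0.593 = 0.456. The same sum gives 0.496 at p = 0.45 and 0.527 at p = 0.50. The average is therefore **46%, 50% and 53%**. Counting the rare splits with one patient in a group changes these by less than one point.

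**5. The reduced-SD figure.** Section 8.0 does not say what the 35% is a percentage of. Two raw-scale readings, pooled t-test:

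| Reading | SDs (true, pseudo) | Power at 6/6 | Average over p = 0.40 to 0.50 |
|---|---|---|---|
| Both SDs × 35/50 = 0.7 | 0.175, 0.070 | 81% | 72–78% |
| SD = 35% of each group's mean | 0.154, 0.0805 | 86–87% | 79–83% |

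In the second row, the 40% end is 78% if splits with a single patient in a group count as failures.

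A third reading divides the 91% difference by a 35% SD as if both had one base. It gives 99% at 6/6, but the same reading with the uncorrected 50% SD gives 90%, not 55%, so it is not the calculation behind the plan's baseline.

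**6. Sensitivity to test and scale (SDs not reduced).** Welch averages 49–53%. On the log scale, with lognormal distributions matched to the stated means and SDs (an assumption), the pooled test gives about 65% at 6/6, 62% at 5/7 and 57.5% at 4/8, averaging 58–61%. With one common SD of 0.19 it gives 54% at 5/7 and 51% at 4/8.

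**The case against.** The best defence is that nothing is miscalculated. The 55% reproduces, and its condition, "assuming n=6 per group", stands in the same sentence. This is a 12-patient pilot that already admits low power without correction. At a 50% share, inside the plan's range, the average loss is only 2–3 points. All of that stands: this is a missing sensitivity statement, and a reader who inferred an arithmetic error in the 55% would be wrong.

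The second defence is that the loss comes mainly from pooling unequal variances. Under Welch, power rises at 5/7 and 4/8. With more pseudo- than true progressions, the pooled test has higher nominal power, though with inflated type I error. The plan also allows a log transform when variability depends on the mean, and the log-scale averages exceed 55%. This stands too, so it would be wrong to say that imbalance always costs power. It does not restore the stated 55%, which is a raw-scale pooled-test figure: on that basis the average is 46–53%, and the Welch average is also below 55%.

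Third, much of the shortfall from 90% is present at 6/6 and depends on the meaning of 35%. That is correct. On the log scale with SD at 35% of each mean, 6/6 power is 92%. Averaged over the split, the two readings give about 84% to just under 90% on that scale.

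**Conclusion.** The point holds as a planning statement that should be restated. At the plan's own expected share, Aim 2 has about 46–53% power without SD reduction, against the stated 55%. With reduced SD it has about 72–78% or 79–83% on the raw scale, against at least 90%. These figures assume a binomial split, normal data, the stated means and SDs, and the one-sided pooled t-test. The loss is small near a 50% share and about 10 points near 40%.

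Two stronger readings are not supported:

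- The introduction says "Pseudo-progression occurs in about 20-30% of glioblastoma patients", and a reader might apply that rate here. Its denominator is glioblastoma patients generally, whereas this study enrols only those with an uncertain new or enlarged lesion. For them, section 3.1 gives 40–50%.
- Section 4.1 describes the neurosurgeons as "seeing about 60 patients with recurrent glioblastoma annually", from which a reader might expect mostly true progressions. That phrase describes the clinic pool and says nothing about the split among enrolled patients.

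Nor do the documents give a basis for withholding the test below some minimum group size. Such a rule would also be inconsistent with these averages, which count the tests done in small groups.

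**What to change.** In section 8.0, Aim 2:

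1. Keep 55% as the 6/6 value, but state as the planning figure the power averaged over a binomial split at the 40–50% share of section 3.1: about 46–53% for the one-sided pooled t-test on raw values.
2. Say whether the 35% is a proportional cut in both SDs or a percentage of each group's mean, and restate the figure of at least 90% on the same averaged basis.
3. Name the test (pooled or Welch) and the scale (raw or log) behind each figure, and match them to the Statistical Analysis text. A short table of power at 6/6, 5/7 and 4/8 would let readers see the dependence.

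The cost is a few sentences and slightly less favourable stated figures. Enrolment and procedures are unchanged, and no extra patients are needed.

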The use of a static phantom comprised of multiple objects with different contrast-agent concentrations was originally suggested to correct the variation in quantitating contrast-agent concentrations of tissues (25). However, a static phantom may not serve as a reliable standard for dynamically changing tissue contrast-agent concentration, because a) the movement of contrast agents in vivo causes additional signal reduction that cannot be replicated by a static phantom, b) the number of data points obtained from a static phantom is small, leading to larger fitting errors, and c) most B₁ mapping techniques are T₁ dependent, thus the nominal flip angle delivered to a static phantom with high contrast-agent concentration cannot be accurately measured, especially in high field MRI (\geq 3T) (26-29). Therefore, a perfusion phantom with a varying contrast-agent concentration is required for accurate correction of MRI system-driven error. A few perfusion phantoms have been developed (30, 31), but these phantoms are too bulky to be simultaneously imaged with a human subject. In addition, these large phantoms are costly and not easily operable by typical MRI technologists, limiting the potential for widespread and routine clinical use. We recently developed a perfusion phantom named P4 (Point-of-care Portable Perfusion Phantom) that significantly reduces variation in quantitating the perfusion of human tissues across different MRI scanners (1). Figure 2A is a photograph of the P4 with its dimensions. is composed of top and bottom chambers with a semi-permeable membrane placed between them. Both chambers are filled with degassed/deionized water before use. After starting DCE-MRI, an MRI contrast agent is infused to the top chamber at a constant rate using a syringe pump. contrast agent displaces the water in the top chamber and diffuses to the bottom chamber as shown Our lab-made software automatically segments the entire region of the bottom chamber (ROI), and the mean value within the ROI is calculated automatically, creating contrast enhancement curves (CEC) as shown in Fig. 2C. The dynamic change of contrast concentration in the bottom chamber was linear for 10 minutes (0.11 mM/min), when independently measured using liquid chromatography-mass spectrometry detection (LC-MS) method (32). repeatability of phantom CEC measured by intra-class correlation coefficient (ICC) (33) was larger than 0.99 in all measurements. Please see our paper for more details (1). The P4 is small enough to be imaged with a human subject and is large enough not to suffer from the partial volume effect, thus MRI system-driven error can be detected during human imaging. correction, the within-subject coefficient of variation (wCV) of the volume transfer constant (Ktrans), a DCE-MRI parameter, was about 20%, but after error correction using the P4, the

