
variation was reduced to about 4% (1). Figure 3 shows the K^{trans} values averaged in each of the four organ regions of three volunteers (n=12) when two different 3T MRI scanners were used (1). Before correction, the ICC between the two data sets was 0.89, and the ICC was not improved by static phantom based error correction (ICC=0.86). However, after P4-based error correction, ICC was increased to 0.99. The P4 is easily operable by MRI technologists, thus it has great potential to facilitate multi-site clinical trials employing quantitative DCE-MRI (qDCE-MRI). Of note, the clinical utility of the P4 was recently demonstrated (34). After P4-based error correction, the change of K^{trans} in pancreatic tumors favorably responding to chemotherapy was able to be significantly differentiated from that in non-responding tumors (p<0.0001) (34). Besides, the P4 was able to improve the accuracy in risk stratification of prostate cancer when assessed by qDCE-MRI (35).

[figure not shown]

Fig. 3. K^{trans} maps before and after correction. K^{trans} averaged in each of the four organs of three volunteers (n=12), when Scanner-A (Y-axis) or Scanner-B (X-axis) was used. (A) before or (B. C) after correction using (B) the static phantom (SP) or (C) P4 (1).

We now hypothesize that the variability in qDCE-MRI measurement of glioblastoma across different scanners will be significantly reduced when MRI system-driven error is corrected using the P4, leading to better differentiation between pseudo- and true-progressions. **Figure 4A**

shows the Gaussian distribution of the K^{trans} value of glioblastoma with true- or pseudo-progression in Yun *et al*'s study (13), where the area under the receiver operator characteristic curve (AUC) was 0.76. **Figure 4B** shows the hypothetical result when the measurement variation is reduced fivefold by our method as demonstrated in **Fig. 3**, increasing the AUC drastically (0.76 vs 0.99). The goal of the proposed study is to conduct the preliminary test of this hypothesis before validating our methodology in an extended multi-site clinical trial (e.g., R01 or U01 study).

[figure not shown]

Fig. 4. Hypothetical Gaussian distribution of glioblastoma K^{trans} values of pseudo- and true-progression groups (A) before and (B) after P4-based error correction.

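### Aim 2: with the test that gives the stated 55% power, an SD of 35% gives 81–89% rather than at least 90%, and neither the base nor the source of the 35% is stated

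*Combined protocol and SAP*

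**What the plan says.** The Sample Size Justification in Section 8.0 takes its Aim 2 inputs from one published study. It gives K^trans in the two groups as "0.44±0.25 vs 0.23±0.10 min⁻¹" and describes the spread as a 91% difference "with the standard deviation (SD) of approximately 50% in each group". With 12 patients, assumed to split 6 and 6, it states 55% power at the 5% level "using a one-side two-group student t-test". It then says: "However, if the SD is reduced to ≤35% using the P4, the power will be increased to ≥90" per cent.

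The Statistical Analysis text says that the tumour parameters "will be compared using two-group student t-test", without giving the sidedness. It adds: "Data will be transformed using natural logarithms if the variability is found to be dependent upon its mean value".

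The only figures on how much error the phantom removes are in Section 1.0. The within-subject coefficient of variation (wCV) of K^trans, "a DCE-MRI parameter, was about 20%, but after error correction using the P4, the" "variation was reduced to about 4" per cent. Fig. 3 there describes the earlier experiment as four organ regions in three volunteers, not glioblastoma.

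**The concern.** Two powers are set side by side so that the reader sees a gain from the phantom of 35 points or more. For that comparison to mean anything, both powers need the same test and a clear definition of the SD. The 55% is tied to explicit means and SDs. The figure of at least 90% is tied only to a percentage whose base is not given. Because the condition is an SD of 35% or less, the claim has to hold at exactly 35%.

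The 35% also has no stated origin. The published SDs describe spread between patients, which combines true biological differences with measurement error. The phantom can reduce only the second part.

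The 12 patients are derived under Aim 1. These two powers are therefore the only figures on what the study can show about its primary goal (Section 2.1), and Section 1.0 presents the study as a preliminary test before a multi-site trial. If power is overstated, a non-significant result could be read as the phantom failing a test that was thought to have 90% power.

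**Working it through.** **Inputs (Section 8.0, Aim 2).** Means 0.44 and 0.23, difference 0.21; SDs 0.25 and 0.10; 6 per group; one-sided 5% Student t-test.

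**Method.** Pooled SD s = √((s₁² + s₂²)/2). Noncentrality = 0.21 / (s·√(2/6)). Power is the upper tail of the noncentral t with 10 df beyond 1.812 (one-sided) or 2.228 (two-sided).

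**Step 1: reproduce the 55%.** s = √((0.0625 + 0.0100)/2) = 0.1904. Noncentrality = 0.21/(0.1904 × 0.5774) = 1.910. One-sided power is 55.3%, so the stated figure is right. Two-sided power is 40.8%.

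**Step 2: same test, SD at 35%.**

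| Meaning of 35% | SDs | Pooled SD | Noncentrality | One-sided | Two-sided |
|---|---|---|---|---|---|
| Published SDs × 35/50 | 0.175, 0.070 | 0.1333 | 2.729 | 81.4% | 69.2% |
| Of each group's own mean | 0.154, 0.0805 | 0.1229 | 2.960 | 86.6% | 76.1% |
| Of the average mean, 0.335 | 0.117, 0.117 | 0.1173 | 3.102 | 89.2% | 79.8% |

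Shrinking both published SDs in proportion until the true-progression CV is 35% (0.154 and 0.0616) also gives 89.2%. The second row is the natural reading, because the plan describes the SD as a percentage in each group. On that reading 90% power needs an SD of about 32.9%. On the average-mean reading it needs about 34.5%, and on the scaled reading about 30.3%.

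**Step 3: readings that do exceed 90%.**
- Log scale, with SD √ln(1 + CV²) and difference ln(0.44/0.23) = 0.649: 92.3% at a CV of 35%. The same scale starts at 71.5% at a CV of 50%, or about 65–71% using the published CVs, depending on how the log means are set.
- The 91% difference and the SD both as percentages of one mean: 99% at 35%, but already 90% at 50%.
- Normal approximation, 35% of each group's own mean: 90.6%, but 60.5% at the published SDs, and it is not the stated t-test.

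None of these starts at 55%.

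**Step 4: what the plan's own error figures imply.** Assume that the wCV of 20% falling to 4% applies to these tumours and that variances add. Then a 50% SD becomes √(0.50² − 0.20² + 0.04²) = √0.2116 = 46%.

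Applied to the published SDs:
- True progression: (0.25/0.44)² − 0.0384 = 0.2844, so the CV is 0.533 and the SD 0.2347.
- Pseudo-progression: (0.10/0.23)² − 0.0384 = 0.1506, so the CV is 0.388 and the SD 0.0893.
- Pooled SD 0.1775, noncentrality 2.049, one-sided power 60.4%.

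This is a gain of about 5 points over 55.3%. A fall from 50% to 35% would need removal of an error CV of √(0.50² − 0.35²) = 36% (0.357, or 0.359 if 4% remains). That is nearly twice the 20% quoted.

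**The case against.** The strongest reply is that the 55% and the 90% can be matched to rounding. The pooled published SD, 0.190, is 57% of the average mean. Starting there gives 55.3%, and 90% is reached at about 34.5%, which could have been printed as 35%. This stands in part. The average-mean reading, and the one that shrinks both SDs in proportion, start from the same 55% and miss by less than one point. It would therefore be too strong to say that the two powers cannot be brought together on any basis, or that 81% is the true figure. The 81% comes from the least favourable reading, which leaves the true-progression SD near 40% of its mean (0.175/0.44). Even so, the plan does not state the average-mean base, and even that base falls short at exactly 35%.

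A second reply is that the sentence is conditional, so 35% is already an assumption, and that volunteer wCV figures say little about error in glioblastoma. This also stands in part. A reader might infer that 35% cannot be reached. The documents do not support that: they give no measurement error for the cited study or for these tumours. They give no support for 35% either.

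On sidedness, a reader might see a contradiction between the two parts of Section 8.0. The analysis sentence is silent rather than contradictory. It only needs completing.

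**Conclusion.** The point holds in a limited form. The 55% is right. At an SD of 35%, the same test gives 81–89% depending on the base, and 87% on the natural reading. The gain that follows from 55% is therefore about 26–34 points (31 on each group's own mean), not 35 or more. If the analysis were run two-sided, power would be 41% at the published SDs and 69–80% at 35%.

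The 35% has no stated source. The estimate of about 46%, with about 60% power, rests on two assumptions that the documents cannot confirm: that the volunteer wCV figures carry over to glioblastoma, and that variances add. It shows that the plan's own figures do not lead to 35%, and it is not a forecast.

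A reader might infer that the sample size is wrong. That does not follow, because 12 comes from Aim 1 and does not depend on this sentence. Nor does the arithmetic settle whether the comparison should be called exploratory.

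**What to change.** Replace the last sentence of Aim 2 in Section 8.0 with, for example: *If the P4 reduced the SD to 35% of each group's mean (an assumption; the measurement-error share of the SD in glioblastoma is not known), power would be about 87% with the same one-sided test; if a wCV of 20% fell to 4%, it would be about 60%.* If another base was intended, name it and give its power: 81% for the published SDs scaled by 35/50, or 89% for the average mean.

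In Statistical Analysis, state that this t-test is one-sided at 5%, as in the power calculation. Otherwise quote the two-sided powers: 41% at the published SDs, and 76% at 35% of each group's own mean (69–80% across the bases).

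This rewords two sentences and adds no patients, scans or analyses. The cost is a less favourable stated power.
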